6.2 Patient Subjects

The following is the schedule of events for patients participating in the POC Offices.

Visit	Day	POC Subjects Activities Performed in POC Offices
4 Weeks Prior (5 minutes)	Day -28 (+/- 14 days)	
 • Letter sent to providing study background to patient
2 Weeks Prior (15 minutes)	Day -14 (+/- 14 days)	
 • Potential subjects contacted to introduce and determine interest in the study • Obtain electronic consent signature • Complete Patient Pre-Visit Survey
Visit (35 minutes)	Day 1	
 • Complete Start-of-Visit Triage Case Report • Undergo POC Test • (Provision of Dental Treatment - not part of research protocol) • Complete Patient End-of-Visit Survey • Complete Patient Participation Questionnaire

The following is the schedule of events for patients participating in the LAB Offices.

Visit	Day	POC Subjects
		Activities Performed in LAB Offices
4 Weeks Prior (5 minutes)	Day -28 (+/- 14 days)	
• Letter sent to providing study background to patient
2 Weeks Prior (15 minutes)	Day -14 (+/- 7 days)	
• Potential subjects contacted to introduce and determine interest in the study• Obtain electronic consent signature• Complete Patient Pre-Visit Survey
1 Week Prior (30 - 60 minutes)	Day -7 (+/- 5 days)	
• Provide specimen for PCR (viral) test• Drop specimen off at a UPS store or UPS Dropbox
Visit (20 minutes)	Day 1	
• Complete Start-of-Visit Triage Case Report• (Provision of Dental Treatment - not part of research protocol)• Complete Patient End-of-Visit Survey• Complete Patient Participation Questionnaire

6.3 Unscheduled Visit

Not applicable. For dental patient participants, the study takes place during 1 patient dental visit. For Dental Healthcare Workers, data collection occurs at three specific times over a one-month period: start, mid-month, end of month.

7 STUDY PROCEDURES/EVALUATIONS

In general, the study will include completion of COVID-19 triage case reports, completion of COVID-19 testing, and administration of perception and attitude surveys. The DHCW Start-of-Visit, Mid-Visit and End-of-Visit and the Patient Start-of-Visit triage case report will include recording of temperatures and pulse oximeter reading for participants in both POC and LAB offices. During day 1, the dental visit, normal patient care will be provided to the patient subject.

Group 1- DHCWs in POC Office

Consent Process for Group 1- DHCWs in POC Offices

Within 4 weeks prior to study initiation in the dental office, the National Dental PBRN Node Coordinator will consent the DHCWs in the participating office. The consent will clearly outline participant expectations and offer the opportunity for potential participants to contact the National Dental PBRN Node Coordinator for more information as needed. DHCWs who elect to participate will affirm their willingness to participate by signing the consent form.

Study Procedures for Group 1- DHCWs in POC Offices

Prior to study initiation (Up to 4 weeks prior)

- Complete consent for all DHCW participants

Day 1

- Complete an electronic survey: *DHCW Start of Study Survey*
 - Questions include demographics, PPE used in the office, work practice controls used in the office, importance of triage and testing, importance of PPE measures, perceptions of safety and comfort in the workplace, safety culture in the office, SARS-CoV-2 testing preferences, dentists' role in SARS-CoV-2 testing, and willingness to test in the office
- Undergo a three-part COVID-19 triage screening*
 - Symptom questions
 - Presence or absence of:
 - fever or chills
 - cough
 - shortness of breath or difficulty breathing
 - fatigue
 - muscle and body aches
 - headache
 - loss of taste
 - loss of smell
 - sore throat
 - congestion or runny nose
 - nausea or vomiting
 - diarrhea
 - Temperature check
 - Pulse oximeter reading
- Complete two COVID-19 related tests**
 - SARS-CoV-2 POC test (administered by the PBRN practitioner or designated investigator)
 - A nasal swab will be swept inside the participant's nose (not beyond the nares) to collect the specimen for the SARS-CoV-2 test
 - The office staff will process the specimen in the dental office
 - ELISA Antibody test (specimen collected by the PBRN practitioner, designated investigator or self)
 - A small lancet will create a finger prick to collect a small blood sample for collection using a Mitra cartridge (blood specimen collection device)

- The Mitra cartridge will be packaged by the DHCW and placed in the practice collection box to await shipment to Rutgers
- The sample will be processed by the Public Health Research Institute (PHRI) Lab at Rutgers

Mid-Study- Day 14 (+/- 7 days)

- Undergo a COVID-19 triage screening in the office*
- Complete a SARS-CoV-2 POC test** (administered by the PBRN practitioner or designated investigator)
 - A nasal swab will sweep the inside of the participant's nose (not beyond the nares) to collect your specimen for the SARS-CoV-2 test
 - The office staff will process the specimen

[figure not shown]
End of Study- Day 28 (+/- 7 days)

- Undergo a three-part COVID-19 triage screening*
 - Symptom questions
 - Temperature check
 - Pulse oximeter reading
- Complete two SARS-CoV-2 tests**
 - SARS-CoV-2 POC test (administered by PBRN practitioner or designated investigator)
 - A nasal swab will be swept inside the participant's nose (not beyond the nares) to collect the specimen for the SARS-CoV-2 test
 - The office staff will process the specimen in the dental office
 - ELISA Antibody test (specimen collected by the PBRN practitioner, designated investigator or self)
 - A small lancet will create a finger prick to collect a small blood sample for collection using a Mitra cartridge (blood specimen collection device)
 - The Mitra cartridge will be packaged by the DHCW and placed in the practice collection box to await shipment to Rutgers
 - The sample will be processed by the Public Health Research Institute (PHRI) Lab at Rutgers
- Complete two electronic surveys:
 - *DHCW End of Study Survey*- Questions include importance of triage and testing, importance of PPE measures, perceptions of safety and comfort in the workplace, safety culture in the office, SARS-CoV-2 testing preferences, dentists' role in SARS-CoV-2 testing, willingness to test in the office, and vaccinations
 - *DHCW Participation Survey*- Questions explore perceptions related to study participation including survey and testing logistics

*If any aspect of the COVID-19 triage screening is positive without any preexisting condition which could explain the positive screening (i.e.. a history of hay fever which likely explains sneezing or a report of physical activity which likely explains muscle soreness), the DHCW will be referred to their primary care physician for further testing.

- Positive screening includes having one or more symptoms of unknown origin
- A positive temperature is considered greater than 100.4 degrees F
- A positive pulse oximeter is considered when the blood oxygen saturation level is below 95%

**If the POC COVID-19 test is positive, the DHCW may be dismissed from duties and instructed to consult with their primary care provider for further testing.

Group 2- Patients in POC Offices

Consent Process for Group 2- Patients in POC Offices

Three weeks (+/- 20 days) prior to visit, patients will get an introductory/interest letter, informing them about the study and that they may be receiving a phone call to determine their interest. About two weeks prior to their scheduled dental visit, patients will be contacted by the dental office to determine their willingness to participate in the study. Patients who indicate interest will be sent an email link, which opens the consent. Patients will be able to speak to the PBRN practitioner or approved staff member with any questions or seek clarifications. The consent will clearly outline participant expectations and offer the opportunity for potential participants to contact the office for more information as needed. Participants who elect to participate will affirm their willingness to participate by clicking the *"I agree to take part in this study"* button at the end of the consent form.

Study Procedures for Group 2- Patients in POC Offices

[figure not shown]
Study participants will be asked to do the following:

- Two weeks before the dental visit
 - Complete and sign electronic consent
 - Complete an electronic survey: *Patient Pre-Visit Survey*
 - Questions explore perceptions of safety and comfort, reasons for delaying dental care, concerns about returning to dental care, safety precautions valued, importance of triage and testing, and demographics
 - Launched automatically after the completed consent
- At the start of the Dental Visit
 - Undergo a COVID-19 triage screening in the office*
 - Screening includes symptom questions, temperature check, and pulse oximeter reading
 - Complete COVID-19 POC test** (administered by PBRN practitioner or designated investigator)
 - A nasal swab will be swept inside the participant's nose (not beyond the nares) to collect the specimen for the COVID-19 test
 - The PBRN Practitioner or their designee will process the specimen
- At the End of the Dental Visit
 - Complete two electronic surveys
 - *Patient End-of-Visit Survey*
 - Questions explore perceptions with testing preferences, PPE observed, environmental controls observed, concerns about returning to dental care, safety precautions valued, importance of triage and testing, likelihood of reporting symptoms, dentist's role in COVID-19 testing and vaccinations
 - *Patient Participation Survey*
 - Questions explore perceptions related to study participation including survey and testing logistics

*If any aspect of the COVID-19 triage screening is positive without any preexisting condition which could explain the positive screening (i.e.. a history of hay-fever which likely explains sneezing or a report of physical activity which likely explains muscle soreness), appointment will be postponed, and the participant will be referred to their primary care physician for further testing.

- A Positive screening by reporting one or more symptoms of unknown origin
- A positive temperature is considered greater than 100.4 degrees F
- A positive pulse oximeter is considered when the blood oxygen saturation level is below 95%

**If the POC COVID-19 test is positive, the dental visit may be postponed, and the positive patient participant will be instructed to consult with their primary care provider for further testing.

Group 3- DHCWs in LAB Offices

Consent Process for Group 3- DHCWs in LAB Offices

Within 4 weeks prior to study initiation in the dental office, the National Dental PBRN Node Coordinator will consent the DHCWs in the participating office. The consent will clearly outline participant expectations and offer the opportunity for potential participants to contact the National Dental PBRN Node Coordinator for more information as needed. DHCWs who elect to participate will affirm their willingness to participate by signing the consent form.

Study Procedures for Group 3- DHCW in LAB Offices

Prior to study initiation (Up to 4 weeks prior)

- Complete consent for all DHCW participants

Day 1

- Complete an electronic survey: *DHCW Start of Study Survey*
 - Questions include demographics, PPE used in the office, work practice controls used in the office, importance of triage and testing, importance of PPE measures, perceptions of safety and comfort in the workplace, safety culture in the office, SARS-CoV-2 testing preferences, dentists' role in SARS-CoV-2 testing, and willingness to test in the office
- Undergo a three-part COVID-19 triage screening*
 - Symptom questions
 - Presence or absence of:
 - fever or chills
 - cough
 - shortness of breath or difficulty breathing
 - fatigue
 - muscle and body aches
 - headache
 - loss of taste

- loss of smell
- sore throat
- congestion or runny nose
- nausea or vomiting
- diarrhea
- Temperature check
- Pulse oximeter reading
- Complete two COVID-19 related tests**
 - SARS-CoV-2 PCR viral test
 - Saliva (self-collected) and tongue specimens (collected by PBRN practitioner, designated investigator or self)
 - ELISA Antibody test (specimen collected by PBRN practitioner, designated investigator or self)
 - A small lancet will create a finger prick to collect a small blood sample for collection using a Mitra cartridge (blood specimen collection device)
 - The Mitra cartridge will be packaged by the DHCW and placed in the practice collection box to await shipment to Rutgers
 - The sample will be processed by the Public Health Research Institute (PHRI) Lab at Rutgers

Mid-Study- Day 14 (+/- 7 days)

- Undergo a COVID-19 triage screening in the office*
- Complete a SARS-CoV-2 PCR Viral test**
 - Saliva (self-collected)

[figure not shown]
End of Study- Day 28 (+/- 7 days)

- Undergo a three-part COVID-19 triage screening*
 - Symptom questions
 - Temperature check
 - Pulse oximeter reading
- Complete two SARS-CoV-2 tests**
 - SARS-CoV-2 PCR viral test
 - Saliva (self-collected) and tongue specimens (collected by PBRN practitioner, designated investigator or self)
 - ELISA Antibody test (specimen collected by PBRN practitioner, designated investigator or self)
 - A small lancet will create a finger prick to collect a small blood sample for collection using a Mitra cartridge (blood specimen collection device)
 - The Mitra cartridge will be packaged by the DHCW and placed in the practice collection box to await shipment to Rutgers
 - The sample will be processed by the Public Health Research Institute (PHRI) Lab at Rutgers
- Complete two electronic surveys:
 - *DHCW End of Study Survey*- Questions include importance of triage and testing, importance of PPE measures, perceptions of safety and comfort in the workplace, safety culture in the office, SARS-CoV-2 testing preferences, dentists' role in SARS-CoV-2 testing, willingness to test in the office, and vaccinations
 - *DHCW Participation Survey*- Questions explore perceptions related to study participation including survey and testing logistics

*If any aspect of the COVID-19 triage screening is positive without any preexisting condition which could explain the positive screening (i.e., a history of hay-fever which likely explains sneezing or a report of physical activity which likely explains muscle soreness), the DHCW will be referred to their primary care physician for further testing.

- Positive screening includes having one or more symptoms of unknown origin
- A positive temperature is considered greater than 100.4 degrees F
- A positive pulse oximeter is considered when the blood oxygen saturation level is below 95%

**If the lab processed SARS-CoV-2 test is positive, the DHCW may be dismissed from duties and instructed to consult with their primary care provider for further testing.

Group 4- Patients in LAB Offices

Consent Process for Group 4 - Patients in LAB Offices

Three weeks (+/- 14 days) prior to a scheduled dental visit, patients will get an introductory/interest letter, informing patients about the study and that they may be receiving a phone call to determine their interest. About two weeks prior to their scheduled dental visit, patients will be contacted by the dental office to determine their willingness to participate in the study. Patients who indicate interest will be sent an email link, which opens the consent. Patients will be able to speak to the PBRN practitioner or approved staff member with any questions or seek clarifications. The consent will clearly outline participant expectations and offer the opportunity for potential participants to contact the office for more information as needed. Participants who elect to participate will affirm their willingness to participate by clicking the “*I agree to take part in this study*” button at the end of the consent form.

Study Procedures for Group 4 - Patients in LAB Offices

Study participants will be asked to do the following:

[figure not shown]
- Two weeks before the dental visit
 - Complete and sign electronic consent
 - Complete an electronic survey: *Patient Pre-Visit Survey*
 - Questions explore perceptions of safety and comfort, reasons for delaying dental care, concerns about returning to dental care, safety precautions valued, importance of triage and testing, and demographics
 - Launched automatically after the completed consent
 - Receive a saliva collection kit by mail
- One week before the dental visit
 - Complete a COVID-19 saliva test
 - Spit into a tube
 - Package as directed
 - Drop off the completed test kit at a UPS Store or drop-off box
- At the start of the Dental Visit
 - Undergo a COVID-19 triage screening in the office*
 - Screening includes symptom questions, temperature check, and pulse oximeter reading
- At the End of the Dental Visit
 - Complete two electronic surveys
 - Patient End-of-Visit Survey*

- Questions explore perceptions with testing preferences, PPE observed, environmental controls observed, concerns about returning to dental care, safety precautions valued, importance of triage and testing, likelihood of reporting symptoms, dentist's role in COVID-19 testing and vaccinations
- *Patient Participation Survey*
 - Questions explore perceptions related to study participation including survey and testing logistics

*If any aspect of the COVID-19 triage screening is positive without any preexisting condition which could explain the positive screening (i.e., a history of hay-fever which likely explains sneezing or a report of physical activity which likely explains muscle soreness), the appointment will be postponed, and the participant will be referred to their primary care physician for further testing.

- A Positive screening by reporting one or more symptoms of unknown origin
- A positive temperature is considered greater than 100.4 degrees F
- A positive pulse oximeter is considered when the blood oxygen saturation level is below 95%

**If the lab processed SARS-CoV-2 test is positive, the dental visit may be postponed, and the positive patient participant will be instructed to consult with their primary care provider for further testing.

Reporting and Notification

The results of the POC, LAB, and/ Elisa test will be recorded in the *Testing Case Report* form in REDCap. The PI and/or Chief Protocol Officer will notify the Practitioner of test results. The National Dental PBRN dentist member of the practice will be considered the "Practitioner" of the office and assume the responsibility of notifying test results to the DHCWs and patients in the practice.

For the purpose of this study, a COVID-19 positive result is not considered an adverse event though results of this test will be recorded.

DHCW subjects who test antigen or viral positive or who triage positive without any preexisting medical condition will be instructed to speak to their physicians for a definitive diagnosis and follow-up. If a DHCW is back to work in time for the mid-study testing, the mid-study protocol will be followed. Similarly, if a DHCW can return to work in time for the end-of-study testing, the end-of-study protocol will be followed. In either case, a follow-up call by the PBRN practitioner or designated investigator will be made approximately 1 week after the positive triage finding or test result to record any confirmatory tests which were obtained based upon the advice of the DHCW's physician.

Patient subjects who are COVID-19 antigen or viral positive or who triage positive without any preexisting medical condition, will not be seen for their scheduled dental visit. The subject will be referred to their physician for a definitive diagnosis and follow-up.

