Précis:	We will conduct a feasibility study to develop and assess procedures for improved COVID-19 triage and testing in dental practices to increase safety and perceptions of safety of Dental Health Care Workers (DHCWs) and their patients. Four National Dental Practice-Based Research Network (PBRN) member dentists and their office staff will be recruited to participate as either as a Point of Care (POC) Office or a LAB office based upon preference of the PBRN member dentist. In the POC offices, we will test out procedures for POC/SARS-CoV-2 antigen testing in DHCWs and patients of the practice along with enhanced triage using pulse oximeters. In the LAB offices, DHCWs and patients will test procedures for a saliva-based laboratory SARS-CoV-2 viral test (LAB) along with enhanced triage methods. Based on office recruitment (POC or LAB), viral, antigen and/or antibody COVID-19 tests will be administered to DCHW and patients entering the dental office. In addition, the use of pulse oximeters will be added to the DHCW and patient triage protocol. The feasibility of implementing COVID-related testing and enhanced triage procedures in the dental setting will provide preliminary data to inform a larger network-wide study grant application.
Objectives:	Primary: The primary objective of this study is to assess the feasibility of procedures for both COVID-19 point-of-care and lab-based testing along with enhanced triage in dental offices.
Population:	This study will take place in dental offices, each of which with at least one National Dental PBRN member dentist. DHCWs working in a dental office with a participating National Dental PBRN dentist and their adult patients 18 years old and older will be recruited to participate. In each office, up to 10 DHCWs (dentists, hygienists, assistants and office staff) including the PBRN member dentists and up to twenty (20) patients will be enrolled. In total, up to forty (40) DHCW (dentists, hygienists, assistants and office staff will be enrolled) and eighty (80) patients enrolled.
Number of Sites:	Four (4) National Dental PBRN offices
Study Duration:	Twelve (12) months
Subject Participation Duration:	DHCWs in both POC offices and LAB offices will participate in the study for 1 month. Patients being seen in POC or LAB offices will participate in the study for approximately two (2) weeks.
Estimated Time to Complete Enrollment:	Six (6) months

Schematic of Study Design

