3 OBJECTIVES AND OUTCOME MEASURES

3.0 Feasibility Study Outcomes

Objectives	Brief Description/Justification of Outcome Measure	Outcome Measured By	Time Frame
To Determine DHCW and Patient Willingness to Participate	Willingness to participate is important in determining whether dental offices, DHCW and patients would be willing to participate in a large-scale study	
 Ratio of DHCW agreeing to participate as compared to all DHCW asked to participate Ratio of patients agreeing to participate as compared to all patients asked to participate Thoroughness of consent process and ability to ask questions 	
Willingness to Participate:
 
 DHCW – at time of consent by DHCW consent Patients – at time of consent by patients

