5.3 Strategies for Recruitment and Retention

Target Sample Size: 40 dental care health workers and 80 patients.

Target Sample Size by Gender, Race, Ethnicity, and Age: Study population will be drawn from National Dental PBRN dentist members, their co-workers and patients seen in their office. Any adult 18 years and older meeting the inclusion criteria and not meeting any exclusion criteria will be eligible to participate. It is expected that the mix of gender, race and ethnicity will reflect the patient mix of the participating dental offices.

Study Population: The DHCW study population will be dentists, hygienists, assistants and office staff who work in an office with a National Dental PBRN member dentist. The patient study population will be drawn from the dental practice with the National Dental PBRN member dentist.

Inclusion of Women and Minorities and Individuals of All Ages:

Women: Women will be included in this study.

Minorities: Minorities will be included in this study.

Recruitment Strategies: Four (4) National Dental PBRN practitioners who have 4 or more DHCW in their office will be recruited to participate by the National Dental PBRN Node Coordinator. The Node Coordinator will then recruit DHCWs within the practice to participate. If a practice is unable to consent at least 5 DHCWs, the practice will not participate in the study. Another National Dental PBRN practice will be recruited to participate.

Patients will be sent a letter about 4 weeks prior introducing the study by the PBRN practitioner. The PBRN practitioner or PBRN investigators in the office will reach out to patients by phone about 2 weeks prior to the dental visit. The study will be explained and if the patient is interested, an e-mail link will be sent which will allow the patient to review the informed consent. A phone number will be provided to answer questions.

Recruitment Protocol (All Study Groups):

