The PRBN Node Research Coordinator will recruit PBRN dentist members to participate in the protocol. The PBRN Node Research Coordinator will contact PBRN dentist members to introduce the study and gauge initial interest. The dental office will be enlisted if the PBRN dentist member and 4-9 additional office DHCWs of the practice are willing to participate and the PBRN member is willing to perform the responsibilities of the protocol including enrolling and completing 10 patients. The PBRN practitioner's preference will determine which protocol (POC or LAB) will be followed in the office. In total, two POC offices will participate, and two LAB offices will participate.

Office	Study Group	Protocol	COVID-19 Related Tests (Method)
POC	1- DHCW in POC Offices	POC DHCW Protocol	
• Antigen (nasal swab)• Antibody (capillary blood)
	2- Patients in POC Offices	POC Patient Protocol	
• Antigen (nasal swab)
LAB	3- DHCW in Lab Offices	LAB DHCW Protocol	
• Virus (saliva and/or tongue)• Antibody (capillary blood)
	4- Patients in LAB Offices	LAB Patient Protocol	
• Virus (saliva)

Retention: In order to minimize loss of study participants and/or incomplete data collection, the following activities will take place:

- Node Coordinators will work with National Dental PBRN study participants responsible for recruiting subjects and completing surveys to encourage patient enrollment and study completion.
- Participants will receive compensation.

Compensation and Scheduled Payments: DHCWs who complete the study procedures including the end-of-study survey will receive \$125 each. Patients who complete the LAB study procedures including the post-visit survey will be provided \$100 and patients who complete the POC study procedures including the post-visit survey will be provided \$50.

Additional Plans to Minimize Missing or Incomplete Data: The following will minimize missing or incomplete data:

- When appropriate, REDCap survey data fields are set to "required".
- REDCap validation rules on data fields to limit responses to those which are valid

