11 STATISTICAL CONSIDERATIONS

This is a feasibility study to assess feasibility to conduct study procedures and refine trial study logistics. No sample size calculations are being performed.

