Testing Logistics 
• LAB – saliva SARS-CoV-2 viral test• POC – BD Veritor COVID-19 antigen test• PCR viral SARS-CoV-2 test• ELISA antibody SARS-CoV-2 test	
• Specimen Collection (3 point Likert Scale)
◦ Very easy to collect◦ Easy to collect◦ Not easy to collect• Specimen preparation for shipping (3 point Likert Scale)
◦ Very easy to prepare◦ Easy to prepare◦ Not easy to prepare• Specimen storage (Binary – Easy/Not Easy)
◦ Easy to Store◦ Not easy to store• Timeliness of results (3 point Likert Scale)
◦ Very timeless access to results◦ Timely access to results◦ Access to results not timely• Reporting of results (3 point Likert Scale)
◦ Very easy to access results◦ Easy to access results◦ Not easy to access results
Testing Case Report	
• Completeness (Binary – Yes/No)

Descriptive statistics (frequencies) for all variables will be performed.

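### No rule says which booked patients an office approaches and no log records the rest, so patient willingness, and to a lesser degree completion, may be inflated by selective approach

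*Combined protocol and SAP*

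**What the plan says.** Section 5.3 starts patient recruitment with a letter: "Patients will be sent a letter about 4 weeks prior introducing the study by the PBRN practitioner". The practitioner or investigators in the office then telephone patients about two weeks before the visit. Section 7 repeats the two steps for POC patients (Group 2), the letter "informing them about the study and that they may be receiving a phone call to determine their interest", and the next sentence states that the dental office contacts patients to learn whether they will take part. The LAB patient process (Group 4) is the same in substance.

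Three numbers bear on how many patients an office needs:

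- Section 5.3, Recruitment Protocol: the practitioner must be willing to carry out the protocol duties, "including enrolling and completing 10 patients".
- Protocol Summary, Population: in each office "up to twenty (20) patients will be enrolled".
- Section 5.3: "Target Sample Size: 40 dental care health workers and 80 patients".

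The willingness outcome in Section 3.0 is "Ratio of patients agreeing to participate as compared to all patients asked to participate". Section 3.0 also lists the percentage completing the study. Section 4 names these two percentages as the important outcomes. Section 11 says "No sample size calculations are being performed", and Section 11.1 ends with "Descriptive statistics (frequencies) for all variables will be performed".

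**The concern.** The practice carries out both approach steps and has undertaken to complete a number of patients. The plan does not say which booked adults get the letter or the call, in what order, or what is recorded about those never approached. If an office starts with patients it expects to agree and finish, the ratio of agreeing to asked describes that office's approach as well as its patients' willingness. Counting every person asked does not remove this, because the selection happens before anyone is asked.

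Section 3.0 justifies the willingness measure by the need to know whether offices, staff and patients would join a large study, and the Protocol Summary says the results feed a network-wide application. A figure that is too high would lead that application to plan too little recruitment effort. The gap would be filled by each office during recruitment, and without a log it cannot be repaired afterwards.

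**Working it through.** **1. The plan's own numbers.** There are four offices (Protocol Summary).

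- Cap: 4 × 20 = 80, which reproduces the stated patient target.
- Office commitment: 4 × 10 = 40, half the target.

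Reading 10 as a minimum and 20 as a maximum would be coherent, but the plan does not say so. No power or sample-size formula applies, because none was used.

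**2. Is there a rule for approach?**

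- Who acts: the practice sends the letter and makes the call (Sections 5.3 and 7).
- Which patients: no consecutive, random or all-comers rule. The nearest statement, in Section 5.3, is an expectation that gender, race and ethnicity will mirror the practice, with no mechanism.
- When to stop: a cap of 20 per office, with six months estimated for enrolment. If an office books more than 20 eligible and willing adults in its recruitment period (an assumption), some are left out and nothing says which.
- Trace: no log of patients not approached, frequencies only in the analysis, and no outside site monitoring planned (Section 10).

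**3. Possible size for willingness.** The documents give no rates, so every rate here is assumed. Let c be the share of more cooperative patients on the schedule, s their share among those approached, and pc and pn the agreement rates of the more cooperative and the other patients.

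- True willingness = c·pc + (1 − c)·pn
- Observed willingness = s·pc + (1 − s)·pn
- Bias = (s − c)(pc − pn)

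| pc | pn | c | True | Observed, s = 0.7 | Observed, s = 1.0 | Bias (points) |
|---|---|---|---|---|---|---|
| 0.8 | 0.3 | 0.3 | 45% | 65% | 80% | +20 to +35 |
| 0.7 | 0.4 | 0.5 | 55% | 61% | 70% | +6 to +15 |
| 0.6 | 0.5 | 0.5 | 55% | 57% | 60% | +2 to +5 |

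For the first row, (0.7 − 0.3)(0.8 − 0.3) = 0.20 and (1.0 − 0.3)(0.8 − 0.3) = 0.35. If approach is unselective, s = c and the bias is zero.

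**4. Against sampling error.** Suppose 80 agree of 160 asked (160 is assumed). The 95% Wilson interval is 42.3% to 57.7%, or about ±8 points. The bias in the third row lies inside that, the first row is well outside, and the second straddles it.

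**5. Effect on planning.** In the first row, enrolling 80 needs 80/0.45 = 178 patients asked under unselective approach, but appears to need 80/0.65 = 124 at s = 0.7 or 80/0.80 = 100 at s = 1.0.

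**6. Why a log is also needed.** Asked is not tied to the letter or to the call. With 80 agreeing and an assumed 200 letters and 120 calls, willingness is 80/200 = 40% or 80/120 = 67%.

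**7. Completion.** The same selection could raise completion, but two other features already do so whatever the order of approach: Section 5.1 admits only patients willing and able to follow all procedures, and Section 5.3 pays patients on completing them. The part due to selective approach cannot be separated.

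**The case against.** Several stronger readings are tempting, and the documents do not support them.

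- A reader might infer from the word may in the letter that offices are free to skip letter recipients. That word is only what the letter tells patients. The next sentence of Section 7, and Section 5.3, say without qualification that patients are contacted.
- A reader might infer that offices pick cooperative patients. No section says so. The letter is described as going to patients without restriction, any adult meeting the criteria is eligible, and an all-scheduled-patients reading fits the wording. The practitioner need only be willing to complete 10; the public text states no penalty for falling short and no per-patient payment to the office.
- A reader might infer a known inflation factor. None can be derived, since every rate is assumed and mild selection gives only a few points.
- A reader might infer a biased POC-versus-LAB contrast. No such test of willingness is planned, and any contrast is already confounded by offices choosing their own protocol (Section 4) and by patient payments of $100 (LAB) and $50 (POC).

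It is also true that a consecutive series in four volunteer offices would not by itself estimate network-wide willingness, and that descriptive frequencies suit a feasibility study.

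These points narrow the finding but do not close the gap. Even if every booked adult gets a letter, the cap means calling may stop before the list is exhausted, and the order of calls is unstated. Whichever reading is intended, the text neither requires it nor would show a departure from it.

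**Conclusion.** The point holds as a gap in the recruitment procedure. The plan gives no order of approach and no record of patients not approached, so the willingness ratio is open to upward bias that the planned analysis cannot detect or correct. Completion is exposed to a lesser degree. That selection will occur is not established, and its size is unknown: about 2 to 35 points under the assumed mixtures, zero under unselective approach. The absence of a rule is judged on the public text, from which some pages and the design schematic are missing. This is a cheap improvement worth making before recruitment starts, because it cannot be recovered later. Separately, the per-office numbers (10, and up to 20, against 80 in total) are not related to one another and must be reconciled.

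**What to change.** In Section 5.3 and in the Group 2 and Group 4 consent processes of Section 7:

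- For its recruitment period, each office lists all adults whose visit is booked early enough for both the letter and the call. Short-notice bookings fall outside the list by definition.
- It sends the letter to everyone listed and phones them in appointment-date order, or in a random order supplied by the Node Coordinator, until its enrolment number is reached.
- It logs each patient as lettered, phoned, not reached, ineligible (for example, no computer or internet access), passed over with the reason, agreed, or completed.
- Section 3.0 states which log entries count as asked, and Section 11.1 reports willingness and completion on this series.
- The per-office number is stated once and made consistent across Section 5.3 and the Protocol Summary.

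This needs protocol wording, the existing appointment book and a short log; no test, visit or survey changes. The price is somewhat more calls per enrolled patient and possibly a lower willingness figure. The series would describe these four offices and should be reported as such.
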